4 LIST OF ABBREVIATIONS

Abbreviation	Definition
λ_z	terminal elimination rate constant
ADA	anti-drug antibody
AE	adverse event
AESI	adverse event of special interest
ALT	alanine aminotransferase
ANOVA	analysis of variance
AST	aspartate aminotransferase
$AUC_{0-\infty}$	area under the serum concentration-time curve from zero to infinity
AUC_{0-t}	area under the serum concentration-time curve from zero to the last measurable concentration
AUC_{τ}	area under the serum concentration-time curve from zero to the end of dosing interval
BOR	best overall response
BTC	biliary tract cancer
C_{ave}	average concentration
CC	cholangiocarcinoma
CDE	Center for Drug Evaluation (China)
CFR	Code of Federal Regulations
CI	confidence interval
C_{max}	maximum concentration
C_{min}	minimum concentration
COVID-19	Coronavirus Disease 2019
CR	complete response
CRF	case report form
C_{ss}	steady state concentration
CT	computed tomography
ctDNA	circulating tumor DNA
DCR	disease control rate
DOR	duration of response
ECC	extrahepatic cholangiocarcinoma
ECD	extracellular domain
ECG	electrocardiogram
ECOG	Eastern Cooperative Oncology Group
EOT	end of treatment
EQ-5D	European Quality of Life 5-Dimensions questionnaire
FDA	Food and Drug Administration
HER2	human epidermal growth factor receptor 2
ICC	intrahepatic cholangiocarcinoma
ICH	International Council for Harmonisation
ICR	independent central review
IDMC	independent data monitoring committee
IHC	immunohistochemistry
IND	investigational new drug
ISH	in situ hybridization
LVEF	left ventricular ejection fraction

MedDRA	Medical Dictionary for Regulatory Activities
MRI	magnetic resonance imaging
MUGA	multigated acquisition scan
NCI-CTCAE	National Cancer Institute Common Terminology Criteria for Adverse Events
NMPA	National Medical Products Administration
ORR	objective response rate
OS	overall survival
PD	progressive disease
PFS	progression-free survival
PK	pharmacokinetic(s)
PR	partial response
PRO	patient-reported outcome
PS	performance status
QxW	every 'x' weeks
QOL	quality of life
QTcF	Corrected QT interval using Fridericia formula
RECIST 1.1	Response Evaluation Criteria in Solid Tumors, version 1.1
SAE	serious adverse event
SAP	statistical analysis plan
SD	stable disease
SMQ	Standardised MedDRA Query
SOC	system organ class
TEAE	treatment-emergent adverse event
$t_{1/2}$	half-life
t_{max}	time to maximum concentration
ULN	upper limit of normal
US	United States
WHO	World Health Organization
WHO-DD	World Health Organization Drug Dictionary

5 INTRODUCTION

This Statistical Analysis Plan (SAP) describes the statistical methods, assumptions, and details of the planned statistical analyses to be performed for Study ZW25-203.

6 STUDY DESIGN

6.1 Description

This pivotal, multicenter, open-label, single-arm trial will evaluate the anti-tumor activity of zanidatamab monotherapy in subjects with HER2-amplified, inoperable and advanced or metastatic biliary tract cancer (BTC), including intrahepatic cholangiocarcinoma (ICC), extrahepatic cholangiocarcinoma (ECC), and gallbladder cancer (GBC). Subjects must have received at least 1 prior gemcitabine-containing systemic chemotherapy regimen for advanced disease, and experienced disease progression after or developed intolerance to the most recent prior therapy. New or archival tumor tissue is required from all subjects for HER2 amplification and HER2 protein expression testing at a central lab using in situ hybridization (ISH) and immunohistochemistry (IHC) assays. Subjects may be tested for HER2 status at the central lab any time after diagnosis of advanced or metastatic disease and before study enrollment. Subjects who elect to be pre-screened for HER2 status must sign a separate informed consent for collection, storage, and analysis of the tumor tissue. Once a prospective subject experiences disease progression or develops intolerance to his/her most recent prior therapy, the main consent for the remaining screening assessments must be signed.

[figure not shown]
Two cohorts of subjects will be enrolled:

- Cohort 1, comprising subjects with HER2 amplification by ISH and HER2 overexpression by IHC, i.e., IHC 2+ or 3+
- Cohort 2, comprising subjects with HER2 amplification by ISH and HER2 IHC 0 or 1+

Enrolled subjects will receive zanidatamab, 20 mg/kg given intravenously (IV) every 2 weeks (Q2W) until 1 of the protocol-defined treatment discontinuation criteria are met. The primary endpoint of confirmed objective response rate (ORR) per the Response Evaluation Criteria in Solid Tumors version 1.1 (RECIST 1.1) will be evaluated by independent central review (ICR). Disease response will be evaluated every 8 weeks (Q8W) with a \pm 7-day window, using computed tomography (CT) or magnetic resonance imaging (MRI) scans.

Subjects who discontinue treatment with zanidatamab for any reason should enter the 30-day follow-up period, as well as survival follow-up. The study schema is presented in [Figure 1](#).

Figure 1: Study Design

CT = computed tomography; EOT = end of treatment; IV = intravenous; MRI =magnetic resonance imaging; ZW25 = zanidatamab

* Timed from Cycle 1 Day 1.

** Subjects may be tested for HER2 status any time after diagnosis of advanced or metastatic disease and before study enrollment. Subjects who elect to be pre-screened for HER2 status must sign a separate informed consent for collection, storage, and analysis of the tumor tissue.

*** Every 8 weeks until disease progression or start of subsequent anticancer therapy.

**** Every 3 months until death, lost to follow-up, withdrawal of consent, study completion, or study termination by sponsor.

6.2 Study Objectives and Endpoints

Objectives	Endpoints

Primary:
 
 To evaluate the anti-tumor activity of zanidatamab monotherapy in subjects with advanced or metastatic HER2-amplified biliary tract cancers (BTC) 	
 Confirmed objective response rate (ORR) by the Response Evaluation Criteria in Solid Tumors version 1.1 (RECIST 1.1), assessed by independent central review (ICR)

Objectives	Endpoints

Secondary:
 
 To further evaluate the anti-tumor activity of zanidatamab monotherapy in subjects with advanced or metastatic HER2-amplified BTC To evaluate the safety and tolerability of zanidatamab monotherapy in subjects with advanced or metastatic HER2-amplified BTC 	
 Duration of response (DOR) by RECIST 1.1 assessed by ICR. Proportion of subjects with a DOR \geq16 weeks by RECIST 1.1 assessed by ICR. Disease control rate (DCR) by RECIST 1.1 assessed by ICR. Progression-free survival (PFS) by RECIST 1.1 assessed by ICR. ORR by RECIST 1.1 assessed by investigator. DOR by RECIST 1.1 assessed by investigator. Proportion of subjects with a DOR \geq16 weeks by RECIST 1.1 assessed by investigator. DCR by RECIST 1.1 assessed by investigator. PFS by RECIST 1.1 assessed by investigator. Overall survival (OS) Frequency and severity of adverse events (AEs) Frequency of serious adverse events (SAEs) and deaths Frequency and severity of clinical laboratory abnormalities Frequency of dose modifications of zanidatamab

Objectives	Endpoints

 • To evaluate the pharmacokinetics (PK) of zanidatamab • To evaluate the immunogenicity of zanidatamab 	
 • Serum concentrations of zanidatamab as a function of time post-dosing • PK parameters for single (first) dose and multiple doses • Population pharmacokinetics and exposure-response analyses. To be conducted according to the data analysis plan entitled “Population Pharmacokinetic and Exposure-Response Analysis to Support Regulatory Biologics License Application Submission of Study ZWI- ZW25- 203 in Biliary Tract Cancer” • Frequency, duration, and time of onset of anti-drug antibodies (ADA) and neutralizing antibodies, if applicable

CCI [REDACTED]
 
 ■ [REDACTED] ■ [REDACTED] ■ [REDACTED] ■ [REDACTED] 	
 ■ [REDACTED] ■ [REDACTED] ■ [REDACTED] ■ [REDACTED] ■ [REDACTED]

6.3 Treatment Assignment and Blinding

This is a single-arm study that will enroll subjects into 2 separate cohorts, based on their HER2 status. Prior to the primary analysis for the study, access to the ICR response assessment data will be limited only to a small team as defined in the Data Access Plan for data cleaning purposes to limit potential bias.

6.4 Statistical Hypotheses

This is a single-arm, open-label study. No statistical hypotheses will be tested.

6.5 Determination of Sample Size

This study will enroll approximately 100 subjects: approximately 75 subjects in Cohort 1 and approximately 25 subjects in Cohort 2. No formal sample size calculations were performed. Approximately 75 subjects will be enrolled in Cohort 1 to evaluate the primary endpoint of confirmed ORR for the primary analysis of efficacy. The 2-sided, exact Clopper Pearson binomial 95% confidence intervals (CIs) that could be observed with this sample size are listed in [Table 1](#). A minimum of 23 subjects with confirmed objective response from a sample-size of 75 would result in the lower bound of a two-sided, exact Clopper Pearson binomial 95% CI exceeding 20 percentage points.

Table 1: Clopper-Pearson 95% Confidence Intervals for N=75 Subjects

Confirmed ORR		95% CI	
Percent	Responses	Lower	Upper
20.0%	15	11.7%	30.8%
25.3%	19	16.0%	36.7%
30.7%	23	20.5%	42.4%
36.0%	27	25.2%	47.9%
40.0%	30	28.9%	52.0%
45.3%	34	33.8%	57.3%
50.7%	38	38.9%	62.4%

Approximately 25 subjects will be enrolled in Cohort 2 to evaluate the primary endpoint of confirmed ORR as a secondary analysis of efficacy. The 2-sided, exact Clopper-Pearson binomial 95% CIs that could be observed with a sample size of 25 subjects are listed in [Table 2](#).

Table 2: Clopper-Pearson 95% Confidence Intervals for N=25 Subjects

Confirmed ORR		95% CI	
Percent	Responses	Lower	Upper
20.0%	5	6.8%	40.7%
24.0%	6	9.4%	45.1%
28.0%	7	12.1%	49.4%
32.0%	8	15.0%	53.5%
36.0%	9	18.0%	57.5%
40.0%	10	21.1%	61.3%
44.0%	11	24.4%	65.1%
48.0%	12	27.8%	68.7%

With a sample size of 100 subjects (Cohorts 1 and 2 combined), the probabilities of detecting 1 or more treatment-emergent adverse events (TEAEs) for various frequencies of occurrence in this population are listed in [Table 3](#).

Table 3: Probabilities of Detecting ≥ 1 Adverse Events

Frequency of Adverse Event	Binomial Probability
0.1%	10%
1%	63%
5%	99%

6.6 Timing of Analyses and Interim Analyses

No interim analyses of the efficacy will be performed for this study. The primary analysis of efficacy will be performed approximately 6 months after the last subject has been enrolled into Cohort 1.

Safety and study conduct will be monitored throughout the study by an independent data monitoring committee (IDMC). The committee is tasked with monitoring the safety of participants in this study through regular and/or ad hoc meetings. The first IDMC meeting will be held after the first 25 subjects have received at least 1 dose of study treatment; subsequent meetings will be held quarterly to review cumulative safety data to identify any potential new safety signals. Additional IDMC meetings will be held at least 28 days after the tenth subject enrolled in China has received 1 dose of zanidatamab to review safety. The IDMC will be responsible for making recommendations to the sponsor as to appropriate study direction; further details will be provided in the IDMC charter.

7 STATISTICAL CONSIDERATIONS

7.1 Analysis Sets

For the purposes of analysis, the subject analysis sets are defined in [Table 4](#).

Table 4: Analysis Sets

Analysis Set	Description
Screened	All participants who sign the main study informed consent
Enrolled	All participants who sign the main study informed consent, were eligible for the study, and received approval to enroll at the end of Screening.
Safety	All safety evaluable subjects enrolled in Cohorts 1 and 2. A subject is considered safety evaluable if they received any amount of zanidatamab.
Efficacy	The following Efficacy Analysis Sets will be evaluated for this study: 
Cohort 1 (Primary) - Includes all safety evaluable subjects enrolled in Cohort 1. The primary analysis of efficacy will be performed using this analysis set.Cohort 2 - Includes all safety evaluable subjects enrolled in Cohort 2.
Response Evaluable	The following Response Evaluable Analysis Sets will be evaluated for this study: 
Cohort 1 - Includes all response evaluable subjects enrolled in Cohort 1Cohort 2 - Includes all response evaluable subjects enrolled in Cohort 2 Response Evaluable includes all subjects in the safety analysis set with measurable disease at baseline and at least 1 evaluable post-baseline disease assessment (per RECIST 1.1) or who discontinued study treatment due to death or unequivocal clinical progression.
Pharmacokinetics	All subjects who received any amount of zanidatamab and have at least 1 post-baseline PK assessment.

Immunogenicity	All subjects who received any amount of zanidatamab and have both baseline ADA and at least 1 post-baseline ADA results available
----------------	---

7.2 Subgroups

The following subgroups may be evaluated for efficacy. Subgroups with 5 or fewer subjects may not be evaluated.

- Disease subtype
 - Gallbladder cancer (GBC)
 - Intrahepatic cholangiocarcinoma (ICC)
 - Extrahepatic cholangiocarcinoma (ECC)
- . Intolerance to the most recent prior therapy
 - Yes
 - No (progressed on the most recent regimen)
- Number of prior regimens for treatment of metastatic disease
 - Less than 2 regimens
 - 2 or more regimens
- HER2 expression
 - Cohort 1
 - IHC3+
 - IHC2+
 - IHC Result Not available
 - Cohort 2
 - IHC1+
 - IHC0
- Geographic region
 - North America (Canada, US)
 - Asia (China, South Korea)
 - Other (Chile, France, Italy, Spain, UK)
- Sex (Female, Male)
- Age
 - <65 years
 - ≥65 years
 - <75 years
 - ≥ 75 years
- Baseline ECOG
 - ECOG = 0
 - ECOG = 1

- Disease stage at baseline (study entry)
 - Stage IIb and Stage III
 - Stage IV
- Race
 - Asian
 - Non-Asian

7.3 Handling of Missing Data

7.3.1 Cohort Assignment

Subjects with missing or indeterminate IHC results will be assigned to Cohort 1. The number and proportion of subjects with missing IHC results will be presented.

7.3.2 Efficacy Data

Partial or Missing Dates

Partial or missing death dates, tumor assessment dates, dates of last contact, dates of onset of post-study treatment anti-cancer therapy, and dates used in computing secondary efficacy endpoints will be imputed as follows:

- Missing day only: For partial dates with only the day of the month missing, the day will be imputed as the 15th day of the month, provided that a preceding date of interest does not occur on/after the 15th day of the month. If the preceding date does occur on/after the 15th day in the same month, then the missing day will be imputed as half the distance between the preceding date and the end of the month.
- Missing month and day: For partial dates with the month and day missing, the month and day will be imputed as July 1st, provided that a preceding date of interest does not occur in the same year. If the preceding date occurs in the same year, then the month and day will be imputed as half the distance from the preceding date to the end of the known year.
- Missing month, day, and year: Where appropriate, specific rules for handling completely missing dates are described in the applicable endpoint and analysis section.

In situations where the above rules result in an illogical time (e.g., negative study day, negative cycle day, etc.) the date will be imputed as EOT date + 1 day.

Missing Post-Baseline Assessments

For RECIST based endpoints, subjects without any post-baseline tumor assessments will be handled as follows:

- For the analysis of PFS, subjects will be handled as described in [Table 6](#).
- Subjects with no evaluable post-baseline response assessments will be considered as Not Evaluable (NE) for best overall response.

7.3.3 Quality of Life Data

There will be no imputation of missing data for either the EQ-5D or BPI.

7.3.4 Safety Data

7.3.4.1 Adverse Event Start Dates

For AEs where the date of onset is during or after administration of the first dose of study treatment, missing or partial start dates will be imputed as the earliest possible date that is on or after the date of the first dose of study treatment (zanidatamab). For events indicated on the CRF as occurring prior to first dose of study treatment, missing or partial dates will not be imputed.

- Missing day only: If the start date and date of first dose share the same month and year, the missing start day will be imputed as the day of first dose. If the start date month is after the month of first dose, day will be imputed as the 1st (i.e., 01-*MMM*-*YY*).
- Missing month and day: If the start date and date of first dose share the same year, day and month will be imputed as the day and month of first dose. If the start date year is after the year of first dose, the month and day will be imputed as January 1st (i.e., 01-*JAN*-*YY*).
- Missing month, day, and year: Missing start dates will be imputed as the date of first dose.

7.3.4.2 Adverse Event End Dates

Missing or partially missing end dates for AE which are known to have resolved will be imputed as follows:

- Missing day only: The day will be imputed as last day of the month (e.g., 31-*MMM*-*YY* or 30-*MMM*-*YY*). The AE end date is then imputed as the minimum of {last day of the month} and {death date}. If the month and year are the same as the data cutoff date month and year, then the data cutoff date will be used as the imputed AE end date.

- Missing month and day: The missing month and missing day will be imputed as December 31. The AE end date is then imputed as the minimum of {Dec 31 of the year}, {death date}, {End of Study date} and {data cutoff date}.
- Missing month, day, and year: The AE end date will be imputed as the minimum of {death date}, {End of Study date} and {data cutoff date}.

7.3.5 Pharmacokinetic Data

Missing values for PK measurements will be listed as missing and excluded from the calculation of summary statistics. If a PK result is available but the collection time is missing or incomplete, then the nominal collection time indicated in the case report form (CRF) will be used. Sample concentrations that are below the lower limit of quantification (LLOQ) will be shown as less than reportable (<LLOQ) in the individual subject listings and imputed as follows for the purposes of calculating summary statistics and producing graphical summaries:

- If the sample was collected prior to the 1st dose of zanidatamab, then the value will be imputed as zero.
- If the sample was collected after the 1st dose of zanidatamab, then the value will be imputed as the LLOQ.

Exclusion of PK data will be based on documented errors in dosing, sample labeling, sample handling, or bioanalysis. Excluded data will not be used in calculations for any tabulated or graphical summaries. Subjects that were not dosed or were not dosed in accordance with their assigned dose level, will be excluded from any tabulated or graphical summaries. Biologically implausible data may also be excluded in the summaries; however, all individual data will be listed and any exclusion, along with the corresponding rationale, will be noted.

7.4 Multicenter Studies

The primary set of analyses will be conducted using pooled data from all sites. There are multiple sites in this study, however it is not anticipated that any center will accrue enough subjects to warrant an analysis by center.

7.5 Adjustments for Covariates

No adjustments for covariates will be performed.

7.6 Multiple Comparisons, Multiplicity, and Multiple Testing

No adjustments for multiple comparisons will be performed.

7.7 Data Conventions, Definitions, and Formulas

The following data conventions will be used for the tables, listings, and figures.

- **Study drug:** Zanidatamab or ZW25
- **Baseline value of a study assessment:** The last non-missing observation prior to the first dose of zanidatamab, unless otherwise specified. If both a planned assessment and repeat assessment (e.g., retest) meet the above criteria and were collected on the same date and time, the repeat assessment will be used as baseline.
- **Study day of a study event or assessment:** The difference between the date of the event or assessment and the date of first dose plus 1 for events or assessments occurring on or after the day of first dose. For example, if an event occurs on 08JUN2014 and the date of first dose was 06JUN2014, the study day of the event is 3. For events or assessments occurring before the day of first dose, it will be the difference between the date of the event or assessment and the date of first dose. For example, if an event occurs on 05JUN2014 and the date of first dose was 06JUN2014, the study day of the event is -1, which is consistent with the Study Data Tabulation Model (Version 3.2) from Clinical Data Interchange Standards Consortium (CDISC).
- **Pre-treatment Period:** Period of time prior to first dose of zanidatamab
- **Study Treatment Period:** Period of time that begins on the date of the first dose of zanidatamab through 30 days after the date of the final dose of zanidatamab.
- **Post-treatment Follow up Period:** Period of time that begins 1 day after EOT and ends at End of Study (EOS).
- **Disease Assessment dates:** In the event, radiographic assessment for a subject occurs over multiple days for a visit, the following convention will be used to determine the date of the RECIST disease response assessment:
 - For a response of Progressive Disease (PD), the date of the earliest radiographic scan will be used.
 - For responses other than PD, the date of the latest radiographic scan will be used.
- **Duration of zanidatamab Treatment:**

Duration of zanidatamab treatment is defined as the difference in days between date of first dose and the earliest of the following dates:

 - Date of last dose + 14 days
 - Date of death
 - Date of subsequent anticancer therapy

Duration (days) = (Earliest date above) – (date of first dose) + 1.

- **Total Cumulative Dose:**

Total cumulative dose (mg) = sum of all doses (mg) received during the entire treatment period duration.

- **Actual Dose Intensity (ADI):**

ADI is the actual dose (mg/kg) per week that the subject received over the entire treatment period. For calculating ADI, the treatment period is defined as time from the first dose of study drug to date of last dose + 14 days, regardless of death status during this period.

- **Intended Dose Intensity (IDI):**

IDI is the intended dose of drug (mg/kg) per week

- **Relative Dose Intensity (RDI):**

RDI is the percent of the intended dose intensity over the entire treatment period:

$$RDI = \frac{ADI \times 100}{IDI}$$

8 STATISTICAL METHODOLOGY

8.1 Trial Details

The following information will be summarized for the safety analysis set unless otherwise specified.

8.1.1 Enrollment

The following study enrollment information will be summarized, for all screened subjects.

- Number of subjects treated and the percentage Number of screen failures and the percentage Number and percentage of subjects enrolled and treated in each region and country.
- Screen failures
 - Demographic variables: age, gender, race, country, and ethnicity.
 - Number and percentage of subjects who failed screening by reason.
 - Number and percentage by region and country
- A listing of subjects who failed screening will also be produced, with reasons for screen failure and available demographic information.

In addition, the following summaries will be provided for treated subjects.

- Number and percentage of subjects enrolled and treated in each cohort.
- .

8.1.2 Subject Disposition

The following disposition information will be summarized.

- Number and percentage of subjects who discontinued zanidatamab and the associated reasons for discontinuation.
- Number and percentage of subjects who discontinued study and the associated reasons for discontinuation from the study
- Number and percentage of subjects actively in post-treatment (survival) follow-up.
- Number of subjects in each analysis set
- Duration of study follow-up, defined as the time from first dose to the data cut off date.

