6.7. Survival Follow-Up

Subjects will be followed for survival after discontinuation of study treatment via telephone calls, medical records, and/or clinic visits approximately every 3 months (± 14 days; month = 30 days) after the last follow-up visit or as directed by the sponsor until death, lost to follow-up, withdrawal of consent, study completion, or study termination by the sponsor. Subsequent anti-cancer therapies initiated during follow-up will also be collected, if available.

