9.4.6.6. Overall Survival

OS is defined as the time from the first dose of study treatment until the date of death from any cause. Subjects who are alive at the time of analysis or were lost to follow-up will be censored at the date they were last known to be alive (i.e., right censored). Details of the censoring scheme for the analysis of OS and imputation methods for partial or missing dates of death or last contact will be described in the SAP.

Kaplan-Meier plots and estimates of the quartiles and their corresponding 95% CI will be computed.

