8.2.6 Duration of Response

DOR is defined as the time from the first confirmed objective response (CR or PR) to documented PD per RECIST 1.1 or death from any cause. Subjects who are alive and have not progressed at the time of the analysis will be censored at the time of their last tumor assessment that was a CR, PR, SD, or non-CR/non-PD. The same censoring rules outlined in [Table 6](#) for PFS will be applied to DOR with date of first dose replaced by date of first response. DOR will be calculated based on the ICR response assessments and separately for the investigator response assessments. Only subjects who achieve a confirmed objective response will be included in the analysis of each endpoint.

DOR will be analyzed using Kaplan-Meier methodology and a Kaplan-Meier plot of DOR will also be provided. Kaplan-Meier estimates of the quartiles (median, 25th and 75th) will be computed. Two-sided 95% CI for the quartiles using the Brookmeyer and Crowley method (Brookmeyer and Crowley 1982) with log-log transformation (Collett 1994) will be presented. Tumor assessment dates will be imputed as described in [Section 7.3](#). In the event there are too

few confirmed responses to generate Kaplan-Meier estimates, DOR may be summarized descriptively (i.e., mean, median, standard deviation, minimum, and maximum).

The proportion of subjects with a DOR \geq 16 weeks and the corresponding two-sided, exact Clopper Pearson binomial 95% CI will also be calculated. In addition, the Kaplan-Meier probability and corresponding 2-sided 95% CI at Week 16 will be calculated.

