8.2.7 Overall Survival (OS)

Overall survival (OS) is defined as the time from the first dose of study treatment until the date of death from any cause or date last known alive for those who did not die.

Specifically,

$$\text{OS} = \text{Date of death or date last known alive} - \text{Date of first dose} + 1$$

Subjects alive at the time of analysis will be considered as censored on the date the subject was last known to be alive (i.e., date of last contact). Subjects lacking data beyond the day of first dose will have their survival time censored on the date of first dose (i.e., OS duration of 1 day). Partial or missing dates of death dates and last known alive date will be imputed as described in [Section 7.3.2](#). If resulting imputed death date is on or before last known alive date, then death of death will be set to last known alive date + 1 day. Details of the censoring scheme are described below in [Table 7](#).

Table 7: Censoring and Event Scheme for OS

Scenario	Progression/Censor Date	Outcome
Not known to have died by data cutoff date	Date last known alive	Censored
Death	Death date	Death

Completely imputed dates (e.g., the analysis cut-off date programmatically imputed to replace the missing end date of a dose administration record) will not be used to derive the last known alive date.

Kaplan Meier estimates of the survival curve and quartiles will be calculated. The 2-sided 95% CIs for the quartiles will be calculated using the Brookmeyer and Crowley method (Brookmeyer and Crowley 1982) with log-log transformation ([Collett 1994](#)). Additionally, the probability of survival at timepoints from 3 months to the end of the follow-up period will be reported.

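### The SAP's duration of study follow-up is potential follow-up: it runs to the data cut-off for every treated subject, so it does not respond to withdrawal, loss or late contact

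*SAP*

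**What the plan says.** SAP 8.1.2 (Subject Disposition) lists "Duration of study follow-up, defined as the time from first dose to the data cut off date". The population is set in SAP 8.1: "The following information will be summarized for the safety analysis set unless otherwise specified". The safety set is all treated subjects in both cohorts. The definition does not stop at death, withdrawal, loss to follow-up or last contact.

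The cut-off is tied to Cohort 1 (SAP 6.6): "The primary analysis of efficacy will be performed approximately 6 months after the last subject has been enrolled into Cohort 1".

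The efficacy sections use different end dates:

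- **OS.** SAP 8.2.7: "Subjects alive at the time of analysis will be considered as censored on the date the subject was last known to be alive". It also rules out a wholly imputed date, with the cut-off date as its example, as a source for the last-known-alive date. Protocol 9.4.6.6 applies the last-known-alive rule to lost subjects as well: "Subjects who are alive at the time of analysis or were lost to follow-up will be censored at the date they were last known".
- **DOR.** The progression-free survival (PFS) censoring rules "will be applied to DOR with date of first dose replaced by date of first response" (SAP 8.2.6), so the clock starts at first response and censoring is at an adequate tumour assessment.

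Survival contact after treatment is made "via telephone calls, medical records, and/or clinic visits approximately every 3 months" (Protocol 6.7), with a window of 14 days either way, or as the sponsor directs. The list in SAP 8.1.2 also includes "Number and percentage of subjects who discontinued study and the associated reasons for discontinuation from the study" and the number still in survival follow-up.

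**The concern.** In a single-arm trial with no hypothesis test, readers use median follow-up to judge how mature DOR, PFS and OS are. The planned figure would be the same whether every subject was traced to the cut-off or many had dropped out of sight. A Cohort 1 subject lost at day 14 is credited with at least about 183 days (6 × 30.44), roughly 13 times the time observed (183 / 14).

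The SAP will not let a programmed cut-off date stand in for a subject's last known alive date in the OS analysis, yet it gives every subject that date in the follow-up summary. The stated follow-up therefore need not match the data behind the OS curve. For DOR, it also counts time before any response existed.

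**Working it through.** The documents state no follow-up figure, accrual period or loss rate, so there is nothing to reproduce. The check asks what moves the planned statistic, what moves the reverse Kaplan-Meier median, and how far apart they can be.

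**Inputs.** From the documents: cut-off 6 months after last Cohort 1 enrolment (SAP 6.6); survival contact about every 3 months (Protocol 6.7); median OS 6.2 months as one illustration, the chemotherapy arm of the randomised second-line trial cited in Protocol 1.2. Assumed: uniform accrual over A = 12 or 18 months; median OS 12 months as the second illustration; exponential death and loss; loss hazard λ = 0 or 0.02 per month; last contact 0 to 3 months (uniform) before the cut-off.

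**Step 1: planned statistic.** Cut-off minus first dose is uniform on (6, A + 6). Its median is 6 + A/2, or 12.0 months (A = 12) and 15.0 months (A = 18), whatever the deaths or losses.

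**Step 2: reverse Kaplan-Meier, contact up to the cut-off.** With deaths censored, the curve estimates, for t ≥ 6,

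G(t) = [(A + 6 − t)/A] × exp(−λt),

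and the median solves G(t) = 0.5. The death hazard does not appear.

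- λ = 0: t = 6 + A/2, the same 12.0 and 15.0 months. The difference is nil, although 49% to 78% of simulated subjects have died by the cut-off.
- λ = 0.02, A = 12: t = 10.59, since (7.41/12) × exp(−0.2118) = 0.50. Difference 1.4 months.
- λ = 0.02, A = 18: t = 12.46, since (11.54/18) × exp(−0.2492) = 0.50. Difference 2.5 months.

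**Step 3: add the contact lag.** Deaths up to the cut-off are taken as recorded, and other subjects not lost are censored at last contact. This was simulated with 4 million subjects per setting. Medians in months:

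| Accrual | Median OS | Planned statistic | Reverse KM: no loss, no lag | Lag only | Loss only | Loss and lag | Largest difference |
|---|---|---|---|---|---|---|---|
| 12 | 6.2 | 12.0 | 12.0 | 11.3 | 10.6 | 9.9 | 2.1 |
| 12 | 12 | 12.0 | 12.0 | 10.9 | 10.6 | 9.6 | 2.4 |
| 18 | 6.2 | 15.0 | 15.0 | 14.7 | 12.5 | 12.0 | 3.0 |
| 18 | 12 | 15.0 | 15.0 | 14.1 | 12.5 | 11.7 | 3.3 |

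Lag alone accounts for about 0.3 to 1.1 months; loss and lag together for about 2.1 to 3.3. If deaths since the last contact are also unknown at the cut-off, lag alone gives 1.5 months, and the two together give 2.7 (A = 12) and 3.8 (A = 18).

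**Step 4: the DOR clock.** Six months is about 26 weeks. Scans are every 8 weeks (SAP 8.2.3, note to Table 6). For the last Cohort 1 subject:

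- response at week 8: at most 26 − 8 = 18 weeks of follow-up from response;
- response at week 16: at most 26 − 16 = 10 weeks, short of the 16-week DOR endpoint.

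**The case against.** The other side has a good deal of force.

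- The quantity is defined openly. It is one descriptive line under disposition and enters no efficacy analysis. This stands.
- Loss is not hidden. The same list gives study discontinuations with reasons, and Protocol 4.4.2 names loss to follow-up and withdrawal of consent among them. This stands, but counts and reasons do not show when subjects left or how long the rest were followed.
- The lag may be small. Subjects on treatment are dosed every two weeks, and Protocol 6.7 lets the sponsor direct survival contact, so a status check at the cut-off is possible. This stands as a possibility; I find no such check planned in either document.

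A reader might also infer four stronger things that the documents do not support:

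- *Early deaths inflate the figure.* They do not. A death is a complete OS observation, and Step 2 shows that the death hazard drops out.
- *Subjects gone in week 2 make DOR look mature.* They are not in the DOR analysis, which takes confirmed responders only. The DOR issue is the start of the clock.
- *OS, PFS or DOR estimates are biased by this definition.* Each has its own censoring rule and none uses this quantity.
- *Everyone has at least 6 months of potential follow-up.* That floor holds for Cohort 1 only. The summary covers both cohorts, and the cut-off is not tied to Cohort 2 enrolment.

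**Conclusion.** The point holds as a reporting defect. SAP 8.1.2 labels potential follow-up as study follow-up, credits withdrawn and lost subjects and the time since last contact up to the cut-off, and so departs from the last-known-alive rule in SAP 8.2.7. It is the only follow-up duration statistic I find in the SAP, parts of which are redacted.

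The overstatement against the reverse Kaplan-Meier median is conditional: nil with no loss and no contact lag, rising to about 3.3 months at 18 months' accrual, median OS of 12 months, 2% monthly loss and a 0 to 3 month lag. Only the 6-month cut-off rule, the contact interval and the 6.2-month OS illustration come from the documents; the rest is assumed. The DOR arithmetic in Step 4 needs no loss assumption. The correction is worth making because it is nearly free and changes a figure that readers rely on.

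**What to change.** In SAP 8.1.2:

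1. Rename the present quantity 'potential follow-up' and keep it.
2. Add the reverse Kaplan-Meier median follow-up for OS, by cohort. Deaths are treated as censored, and all other subjects end at the last-known-alive date already derived under 8.2.7.
3. Add the reverse Kaplan-Meier median follow-up from first response for confirmed responders, using the end dates already set for DOR in 8.2.6, with progression or death treated as censored.

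All the variables are already needed for the planned OS and DOR analyses. The cost is a wording change and one or two table rows. The downside is that the quoted follow-up may be shorter than the present definition would give.
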